7.10 Study Site Monitoring

No on-site monitoring will be conducted for this study. Study sites will be contacted by i3 staff out of the Study Management Center (SMC) at regular intervals during the course of the study to remind them to enter resource utilization data into the CRF. These contacts will include the pre-study qualification, initiation, interim monitoring, and close-out requirements. In addition, sites will be called every 3 months after enrollment visit of a patient to remind them to send out the survey package to the patient.

Study monitoring is conducted remotely via telephone contact. Sites will be asked to send in their CRFs on a regular basis to allow for early identification of potential issues.

Sites will be informed via phone of proper close-out activities after all data has been captured appropriately and no data issues are open in both studies. Final documents will be collected as needed.

8 DATA MANAGEMENT

i3 data management activities will comply with all applicable regulatory requirements and i3 established practices for collection and validation of data and preparation of a reliable database for statistical analysis. The project specific procedures will encompass all of the data management activities associated with the implementation and completion of the study observational plan. A formal data management plan will be prepared for the study. The data management plan will include security and access, data flow, data management, data handling, quality management, and documentation.

8.1 Case Report Forms

Physicians will complete the paper enrolment CRF at the time of the enrollment visit. At month 6 and month 12 the physician will additionally complete a paper CRF for collection of resource utilization data.

Physicians will provide a copy of the CRF and a copy of the informed consent form to i3. The completed CRFs are AZ Property and i3 Innovus will not disclose them to third parties, except for authorized representatives of AZ or appropriate regulatory authorities, without written permission from AZ. AZ will not receive Protected Health Information (PHI) contained in these CRFs.

The study physician will be responsible for completing, reviewing and approving the portion of the case report form relating to the enrollment visit and follow-up contacts.

8.2 Record Retention

To enable evaluations and/or audits by regulatory authorities or AZ, the study physician will be required to keep records, including the identity of all participating subjects (sufficient information to link records, e.g., CRFs and hospital records), all original signed informed consent forms, copies of all CRFs, medical event reporting forms, and source documents for fifteen years after consenting and enrolling the patient.

9 ADVERSE EVENT

The Investigator should report potential adverse drug reactions as post marketing spontaneous reports to authorities/manufacturer of suspect drug(s) according to local procedures.

10 STATISTICAL ANALYSIS

10.1 Introduction

This section outlines the statistical methods that will be used for this study. A formal statistical analysis plan will be developed based on discussions with AZ. The list of tables to be produced will be part of this analysis plan. All analyses will be conducted using SAS version 9.1 for Windows.

10.2 Study Population

Two study populations are considered: the “log population”, which consists of all GERD patients approached for this study and the “per protocol population”, which consists of all patients enrolled in the study, satisfying to inclusion and exclusion criteria specified in section 5.

The proportion of partial-responders to PPI and analysis of screening failure will be conducted over the log population and the analyses of symptoms, patients reported outcomes, healthcare

resource use, productivity loss and associated costs will be performed on the per protocol population.

10.3 Descriptive Analysis

First, frequency tables reporting the characteristics of the log population, proportion of partial-responders to PPI and reason for exclusion will be prepared.

A descriptive analysis will first be undertaken. For continuous endpoints the following will be reported:

- mean
- median
- standard deviation
- 95% confidence intervals for the mean
- minimum
- maximum
- first and third quartiles.

The distribution plot of the variables will also be presented. For categorical variables, we will report frequency tables and histograms.

The following analysis will be reported by physician type (General practitioner, gastroenterologist) and overall.

- Descriptive statistics will be provided for patients' characteristics (age, gender, height, weight, BMI, smoking status).
- Medical history at study entry will be described using retrospective data collected from the physician. This will include the frequency of co-morbidities in partial responders to PPI (proportion of patients having each type of co-morbidities), time since diagnosis of GERD and treatment history of GERD. The treatment history will be described via the proportion of patients having used each type of healthcare resource use and the mean level of resource use by type (diagnostic test by type, surgery, referral to a specialist, prescribed medication by type, dose and frequency).
- The medical treatment pathways will be further described by reporting the proportion of patients receiving each medication as first, second and third treatment and by reporting the frequency of each possible strategy (defined via the sequence of medications prescribed to the patient).

-
- Symptom frequency and severity scores (based on RDQ-RI and GERDQ) will be reported by visit. Graphs providing the mean score value and 95% confidence interval over time (at visit 1, then 3, 6, 9, 12 months) will be prepared.
 - For each quality of life and patient reported outcomes questionnaires (SF-36, QOLRAD - RI, EQ-5D), item, domain and total scores will be estimated according to the scoring instructions from each questionnaire. Each type of score (item, domain and total) will be reported by visit using tables and graphs indicating the mean value and 95% confidence interval over time.
 - Work productivity loss will be described via the proportion of patients having experienced work absenteeism, presenteeism (presence at work but with a reduced productivity), the mean number of workdays lost and the overall productivity loss because of GERD. These statistics will be reported by visit.
 - Resource use (proportion of patients prescribed each type of healthcare resource and mean level of resource use) will be reported by visit. Proportion of patients receiving prescribed medications and OTC medications will be reported by type of medication. The mean number of treatment days will also be reported.

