4 STUDY DESIGN OVERVIEW

This is a multi-center, 12 months prospective study in France. Approximately 275 adult (18 years or older) patients with GERD who have been identified for the first time as partial responders to optimized PPI treatment will be enrolled at approximately 30 sites in France to obtain an evaluable target sample size of 200 patients, assuming an estimated 30% attrition rate over the course of the study.

Patients will be enrolled at a regularly scheduled office visit. At this regularly scheduled office visit, the study physician or designated staff will invite potentially eligible patients to participate in the study. Patients will be provided with a written study description and copy of the informed consent form to review. Eligible patients who express an interest in participating will be officially enrolled in the study on the day of the office visit.

Enrolled patients will fill out a self-administered paper patient survey during this visit including questions for their quality of life and symptoms severity.

Physicians will complete the enrollment part of the CRF including patient demographics and confirmation of patient's eligibility. They will also keep a log of all newly diagnosed patients with

GERD seen during the enrollment period in order to provide estimates of the ratio of patients with GERD identified for the first time as partial responders to optimized PPI treatment to all newly diagnosed patients with GERD. The physician will follow the patients through a period of 12 months after enrollment collecting data from the patient medical records at baseline, month 6 and month 12.

The patient will receive a set of questionnaires every 3 months during the same 12 month period after the first visit. This survey will include questions relating to resource utilization (over the counter medication and visits to other physicians), as well as questionnaires relating to the patient's quality of life and symptom frequency and severity.

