7 STUDY PROCEDURES

7.1 Site Recruitment

Potential investigators will be identified from a global French database provided by Rosenwald and compiling more than 160 000 physician references. A representative sample of 500 physicians including both general practitioners (family doctors and internists) and specialists, i.e. gastroenterologists, will be extracted and invited to participate in this study. The assumed ratio between specialist and general practitioner is 1:1. A mass mailing will be sent out to gauge investigator's interest and to evaluate their ability to successfully participate.

All interested sites, sorted by region, will be assigned a random number and will then be sorted by ascending order. The first 50 sites will be selected to participate. In case of any change in site's willingness to participate the site number 51 will be contacted to supplement the list and then 52, 53 subsequently.

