7.3 Subject Recruitment

Subjects will be recruited in community practice settings by approximately 50 study physicians in France. The target recruitment goal for each physician is 5 to 6 patients with GERD newly identified as partial responders with an upper limit of 14 per physician. Subjects will be enrolled during a normally scheduled office visit.

Enrollment will be closed once the target enrollment goal of 275 patients has been reached. Study physicians will be notified by telephone and fax memo that recruitment is closed.

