10.6 Multiple regression

To investigate the link between symptom (frequency and severity) and QOL we propose to conduct a number of analyses consisting of correlation analysis, graphical analysis and generalised linear modeling. GLM are selected to account for underlying distribution of endpoint of interest (non-normal). We would model QOL score as a function of patients' characteristics, symptoms, adverse effects and medical history, to quantify the impact of each factor on the QOL impairment. Similar types of analyses would be performed for resource use, productivity losses and costs.

In addition we will develop longitudinal models to understand the evolution of the study endpoints over time to quantify the consequences of reducing the symptom frequency and/or severity in terms of costs, quality of life and utility values. We would use generalized estimating equation modeling to model the study endpoint dynamically and account for the between-patient heterogeneity. Generalised Estimating Equation models would be used here to estimate the heterogeneity between-patients vs within patient and to understand the impact of change in symptoms (reduction of frequency, severity) on study endpoints. These analyses would be performed for HRQOL, utility values, productivity loss, healthcare resource use.

Bivariate analyses will be conducted to assess whether each factor of interest (patients' characteristics and symptoms frequency and severity) significantly affects quality of life, resource use, productivity loss and associated costs. The heterogeneity between sites and between patients will be reported via the analysis of intraclass coefficients.

The results of these preliminary analyses will be used to develop generalized linear mixed model, accounting for the underlying distribution of the modeled endpoints and the clustering of the data (patient's repeated measures nested within sites).

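### Section 10.6 recognises clustering of patients within sites, but the 95% confidence intervals in Sections 10.3 and 10.7 are not said to allow for it

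*Protocol*

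**What the plan says.** Section 10.3 sets out the summary for continuous endpoints. Between the standard deviation and the minimum it lists "95% confidence intervals for the mean", with no variance method. For symptom scores it adds "Graphs providing the mean score value and 95% confidence interval over time", and it plans the same display for the quality-of-life instruments. Results are given by physician type and overall. Section 10.7 plans 95% intervals for the proportion of partial responders by site, by physician type and overall, again with no method.

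Section 10.6 treats clustering explicitly: "The heterogeneity between sites and between patients will be reported via the analysis of intraclass coefficients". It then plans a generalised linear mixed model with repeated measures nested within sites. Nothing carries this over to Sections 10.3 or 10.7.

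On the number and size of clusters the protocol gives two versions. Section 4 says that patients "will be enrolled at approximately 30 sites in France". Section 7.1 says "The first 50 sites will be selected to participate", and Section 7.3 speaks of about 50 physicians, each with a target of 5 to 6 patients, "with an upper limit of 14 per physician". Section 6 expects about 200 of 275 enrolled patients to be analysed, calls the resulting precision satisfactory, and mentions no design effect.

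**The concern.** The study tests no hypotheses. Its primary objectives are to describe resource use, cost, symptoms, quality of life and productivity, so the means and their intervals carry much of the answer. Referral, prescribing and diagnostic work-up depend partly on the recruiting physician. Patients of one physician are therefore likely to resemble each other on these outcomes, and the protocol itself plans to measure such resemblance. An interval that treats the patients as independent then claims more precision than the design provides. The overall proportion of partial responders pools the logs of the same sites and has the same gap. The plan would thus report intraclass coefficients in one section and leave them out of the intervals in another.

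**Working it through.** **The plan's own figures.** No interval width is stated, so none can be reproduced. The only sample-size arithmetic is 275 enrolled with about 30% attrition giving about 200. In fact 275 × 0.70 = 192.5, and 200/275 corresponds to 27.3% attrition, so the figure fits only if the rate is read loosely. The check below uses the stated 200.

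**Inputs from the protocol.** About 200 analysed patients (Section 6); 50 sites (Sections 7.1 and 7.3) or 30 sites (Section 4).

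**Assumptions.** ICC of 0.01, 0.05 or 0.10, since the protocol gives none; one recruiting physician per site; equal site sizes at first.

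**Formulas.**
- Patients per site: m = N / sites, so 200/50 = 4.0 and 200/30 = 6.67.
- Design effect: DE = 1 + (m − 1) × ICC.
- Ratio of correct to simple interval width: √DE.
- Coverage of a simple 95% interval: 2Φ(1.96/√DE) − 1.
- Effective sample size: N / DE.

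Example, 50 sites and ICC 0.05: DE = 1 + 3 × 0.05 = 1.15; √1.15 = 1.072; effective sample size 200/1.15 = 174.

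| Sites | ICC | DE | Correct interval wider by | Coverage of simple interval | Effective N |
|---|---|---|---|---|---|
| 50 | 0.01 | 1.03 | 1.5% | 94.7% | 194 |
| 50 | 0.05 | 1.15 | 7% | 93.2% | 174 |
| 50 | 0.10 | 1.30 | 14% | 91.4% | 154 |
| 30 | 0.01 | 1.06 | 3% | 94.3% | 189 |
| 30 | 0.05 | 1.28 | 13% | 91.6% | 156 |
| 30 | 0.10 | 1.57 | 25% | 88.3% | 128 |

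In standard-deviation units, the simple half-width is 1.96/√200 = 0.139. At an ICC of 0.05 it becomes 0.149 (50 sites) or 0.157 (30 sites).

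**Unequal site sizes.** A target of 5 to 6 with a maximum of 14 leaves room for imbalance. With an assumed coefficient of variation of 0.5 in site size, m in the formula is multiplied by 1 + 0.5² = 1.25. At an ICC of 0.05 the widening becomes 9.5% (50 sites) or 17% (30 sites); at 0.10 it becomes 18% or 32%.

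**The proportion in Section 10.7.** The same formula applies, with m the number of logged patients per site. The protocol does not give that number, so no size can be stated. The intervals for single sites are not affected by between-site clustering.

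**The case against.** The strongest reply is that the protocol names no variance estimator, that Section 10.1 defers to a statistical analysis plan which is not shown, and that the standard error of a descriptive mean is commonly settled there. A reader might infer that the protocol prescribes independence-based intervals and that the published ones will certainly be too narrow. The text does not go that far: it is silent on the method, and the shortfall requires an ICC above zero. What remains is that the protocol raises clustering itself, attaches it to one set of analyses only, and lists the interval within a standard univariate summary, where the ordinary formula is the natural reading.

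A reader might also take the worst case, 275 patients at 30 sites, where an ICC of 0.05 to 0.10 gives intervals 19% to 35% wider and coverage of about 85% to 90%. That uses everyone enrolled, which suits baseline at most, together with the site count that fits the recruitment target less well (275/50 = 5.5 per physician; 275/30 = 9.2).

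A third inference would be that narrow intervals distort the national cost of illness. They do not. Clustering in the standard error leaves the mean unchanged, and Section 10.7 carries no cost interval into the national figure.

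Two further objections have some force. The outcomes for which Section 10.3 specifically promises intervals over time are patient-reported, and site correlation may be weaker there than for prescribing or referral. Reporting by physician type also removes, within each type, any part of the between-site variance that is due to type. Both favour the lower end of the ICC range for those results. Neither makes the ICC zero, and neither helps the overall resource-use means.

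**Conclusion.** The point holds as an inconsistency within the protocol and is of modest size. Clustering is recognised in Section 10.6 and not extended to the descriptive intervals of Sections 10.3 and 10.7. If simple intervals are used, the loss is negligible at an ICC of 0.01 and becomes noticeable from about 0.05, more so at 30 sites than at 50. These figures rest on the assumed ICC, one physician per site, equal site sizes unless stated, and the normal approximation. No point estimate changes, and no test or decision rule depends on the interval width. The change is still worth making, because the intervals accompany the study's main results and the protocol already takes the view that supports it.

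**What to change.** State in Sections 10.3 and 10.7 that 95% confidence intervals, overall and by physician type, use standard errors clustered on site (for example from the SAS survey procedures), with degrees of freedom based on the number of sites. For skewed outcomes, such as resource use and any interval reported for cost, state that a site-level bootstrap will be used. Reconcile the site count between Section 4 and Sections 7.1 and 7.3, since the size of the effect depends on it.

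This needs no new data, patients or visits: a sentence in each section and standard software. The downside is somewhat wider reported intervals. If the ICC proves close to zero, they will hardly change.

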6 SAMPLE SIZE

The target enrollment sample size for this study is 275 patients with GERD. An attrition rate of approximately 30% over the course of the twelve-month data collection period is expected as some patients will not complete and return the follow-up patient surveys, yielding a final sample size of ~200 patients for analysis.

Due to the descriptive objectives of the study, there are no hypotheses to test with statistical methods to predetermine a required sample size. Calculations based on a database study in the relevant patient group indicate that the sample size will result in satisfactory precision in estimates of individual items of resource utilization, symptom load, impact of symptoms on daily life and effect on work productivity.¹⁷ Based on previous similar studies in other but related patient groups the sample size is also deemed to be sufficient to satisfactorily describe common treatment pathways.

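### By-visit symptom and quality-of-life means can mix a change in who responds with change within patients, since about 30% are expected not to return follow-up surveys

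*Protocol*

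**What the plan says.** Protocol section 10.3 gives visit-wise RDQ-RI and GERDQ scores: "Graphs providing the mean score value and 95% confidence interval over time (at visit 1, then 3, 6, 9, 12 months) will be prepared". SF-36, QOLRAD-RI and EQ-5D scores are also tabulated and graphed by visit as means with 95% confidence intervals.

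Section 10.2 assigns these analyses to the population "which consists of all patients enrolled in the study, satisfying to inclusion and exclusion criteria specified in section 5". It sets no condition on completing follow-up.

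Section 6 sets enrolment at 275 and then makes this forecast: "An attrition rate of approximately 30% over the course of the twelve-month data collection period is expected". It puts the loss down to non-return, in that "some patients will not complete and return the follow-up patient surveys", and ends with about 200 patients analysed.

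Section 10.6 adds longitudinal modelling: generalized estimating equations (GEE), then a "generalized linear mixed model, accounting for the underlying distribution of the modeled endpoints and the clustering of the data (patient's repeated measures nested within sites"). The outcomes it names for the longitudinal work are HRQoL, utility values, productivity loss and resource use. Section 10.1 leaves further detail to a formal SAP.

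**The concern.** Symptom load, the impact of symptoms on daily life and HRQoL are primary objectives (section 3.1). The surveys expected to go unreturned are the ones that carry these outcomes. Read together, sections 6, 10.2 and 10.3 place about 275 patients behind the visit-1 point and about 193-200 of the same patients behind the month-12 point.

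A plain mean at each visit cannot tell whether patients changed or whether a different mix of patients answered. If the more symptomatic stop responding, the curve improves with no patient improving; if the less symptomatic stop, it worsens. The printed interval reflects sampling error among responders and does not cover that shift.

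The point is about the summary that the protocol chooses. A missing-data rule can properly wait for the SAP, so its absence here is not the complaint.

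**Working it through.** **Inputs from the protocol.** Enrolled N = 275, attrition approximately 30%, about 200 for analysis (section 6); analysis set of all enrolled eligible patients (section 10.2). The protocol gives no within-patient correlation and no relation between drop-out and score. Both are assumed below.

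**Step 1: the plan's own figure.** 275 × 0.70 = 192.5, against about 200. In reverse, 1 − 200/275 = 27.3%. The gap is rounding of two approximate figures and has no bearing on the point. Both loss rates are carried forward where it matters.

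**Step 2: printed uncertainty.** Half-width of the 95% CI in SD units = 1.96/√n.
- n = 275: 0.118
- n = 200: 0.139
- n = 192.5: 0.141

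**Step 3: shift from composition alone.** If a fraction d is lost and stayers differ from leavers by D (in SD), the mean of those left differs from the mean of everyone by d × D. With d = 0.30:

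| D (SD) | Shift (SD) | Shift / half-width at n = 192.5 |
|---|---|---|
| 0.1 | 0.03 | 0.21 |
| 0.2 | 0.06 | 0.42 |
| 0.3 | 0.09 | 0.64 |
| 0.5 | 0.15 | 1.06 |
| 0.8 | 0.24 | 1.70 |

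The shift equals the half-width at D = 0.141/0.30 = 0.47 SD, or at about 0.51 SD with 27.3% lost.

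**Step 4: simulation with no true change.** 100,000 patients, five visits, correlation 0.6 between any two visits, 30% lost by month 12, and a logistic drop-out model in which higher scores leave more often. True month-12 mean is 0.

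| Drop-out depends on | Slope per SD | Raw month-12 mean | Likelihood repeated-measures mean |
|---|---|---|---|
| Nothing | 0 | about 0 | about 0 |
| Previous observed score | 0.5 | −0.09 | 0.00 |
| Previous observed score | 1.0 | −0.18 | −0.01 |
| Unseen current score | 0.5 | −0.11 | −0.04 |
| Unseen current score | 1.0 | −0.21 | −0.08 |

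A second simulation, of 200 studies of 275 patients with drop-out on the previous score, gives a raw change from visit 1 to month 12 of −0.097 and −0.178 SD. The mixed-model change is +0.008 and −0.001 SD, with a standard error of about 0.06 against 0.07 for the raw means. The sign reverses if lower scores leave more often.

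**Step 5: if only completers were plotted.** With drop-out on the previous score, completers run from −0.11 at visit 1 to −0.09 at month 12 (slope 0.5), and from −0.21 to −0.18 (slope 1.0). The false change nearly vanishes, but the level is wrong from the first visit.

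**The case against.** **The SAP will settle it.** Section 10.1 announces a formal SAP with the list of tables, and n per visit or missing-data handling often sits there. That stands for the missing-data rule. It does not cover the choice of summary, which section 10.3 makes itself, for outcomes whose loss section 6 forecasts.

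**The curves may use only the roughly 200 completers.** Section 6 speaks of that number for analysis, and the protocol nowhere says outright that each point uses those who responded at that visit. But a completers-only set conflicts with section 10.2, and by step 5 it moves the bias to the level. Symptom load is a level.

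**Section 10.6 already handles change over time.** It refers broadly to the study endpoints, and section 10.3 is only a first, descriptive step. A reader might infer that the suitable model is already planned for every curve. The text does not support that: symptom scores enter mainly as explanatory factors, are not among the longitudinal outcomes listed, and nothing links those models to the section 10.3 displays. Unweighted GEE, also planned there, does not in general handle drop-out that depends on earlier scores.

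**The size is assumed.** This stands. The correlation and slopes are not in the protocol. The simulations use unrestricted scores, although entry requires a minimum symptom level on the RDQ-RI, and they treat loss as permanent, although non-return may be intermittent. Section 7.8 plans a second mailing and possible patient calls, which may reduce loss; the protocol still expects about 30%.

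**Conclusion.** The concern holds in conditional form. As sections 6, 10.2 and 10.3 stand together, the plotted means rest on a shrinking set of patients. If non-return is related to score, they can mix change in who responds with change within patients. The size is roughly 0.1 to 0.2 SD at month 12, against a 95% CI half-width of about 0.14 SD. It rests on about 30% loss, a correlation of 0.6 and drop-out slopes of 0.5 to 1.0 per SD.

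A reader might go further and infer that the curves will show a false change, or that they will flatter the course of the disease. The documents do not support either. They give no evidence that non-return depends on score and none on its direction; if it is unrelated to score, the shift is about zero.

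Nor should model-based means be read as a complete cure. They return about zero when drop-out depends on observed scores, but keep −0.04 to −0.08 SD when it depends on the unseen current score. That is still well below the raw shift of −0.11 to −0.21 SD.

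**What to change.** In section 10.3, for the domain and total scores of RDQ-RI, GERDQ, QOLRAD-RI, SF-36 and EQ-5D:

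- Present by-visit means and 95% CIs from a likelihood-based repeated-measures mixed model, with visit as a factor, patient within site, and all returned surveys included. Visit levels follow the assessment schedule of section 7.9 for each instrument.
- Extend the section 10.6 mixed model to the symptom scores for this purpose, and do not rely on unweighted GEE for these means.
- Keep the raw means beside them, with n at each visit.
- Tabulate visit-1 scores of patients with and without a month-12 survey, so the reader can judge whether leavers differ.

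Item-level results can stay as simple descriptive summaries.

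The cost is a little more analysis, with a model class already planned and no new data. The downside is that the model means still assume that drop-out depends only on observed scores, so they reduce the bias but do not fully remove it if that fails.
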